In addition to enrichment with family history, we will perform *APOE* genotyping on potential participants. Although the REVEAL Study has focused on the disclosure of *APOE*, in this research project we do not want to conflate disclosure of an AD risk gene variant with the disclosure of an AD biomarker, so the results of *APOE* genotyping will not be returned to the

participants. Instead, *APOE* genotyping will be used to increase the mix of participants who are $\epsilon 4+$ to at least 50%.

“We will not be sharing the results of subjects’ *APOE* genotyping because we, and each clinical study site, will be blinded to these results. *APOE* results will be only used to enrich our study sample to ensure we are effectively randomizing 50% elevated amyloid scans vs. not-elevated amyloid scans into each intervention arm. These *APOE* results will only be reported to the centralized data site, Boston University, but not the other clinical sites (Brigham and Women’s Hospital, University of Pennsylvania, University of Michigan, and Duke University.”

Recruitment

All four sites have extensive experience in recruiting participants for AD clinical trials, with access to research registries of cognitively normal older individuals willing to participate in AD-related studies. Participants will be recruited using a variety of methods including interactions with family members of patients in memory clinics; review of research registries; clinical trials websites; direct referral from neurologists, geriatricians and local Alzheimer’s Association chapters; and talks in the community. We will post information about this study on our website, and on social media. We will use trifold brochures in clinician offices and at appropriate forums. The study will be mentioned in grand rounds, local clinic presentations on AD, and media interviews.

No “cold calls” will be made directly to any potential participant, whether identified from a patient database or medical record, without the consent of the patient and the patient’s primary physician or specialist.

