We will include all ethnic groups and men and women equally as part of this study. The study population will include both male and female healthy participants, 65 to 80 years of age. There is an increased ratio of women to men in AD, and it is anticipated that our recruited sample will reflect this ratio. Since AD affects individuals from all ethnic and racial backgrounds, every effort will be made to ensure a representative sample of preclinical AD participants. African Americans are historically underrepresented in clinical trials, including AD clinical trials. For this study of amyloid imaging disclosure, we will aim to recruit at least 25% African Americans through a partnership with Duke University. We expect that half of the participants at the Duke site will be African Americans.

IV. Subject Enrollment

All individuals who contact our study coordinator will be given a brief overview of the study, including all potential risks and discomforts, and will be asked if they would like to participate. At this initial contact, they will be given the opportunity to ask any questions and to consider whether they wish to participate. They will be informed that refusal to participate will not interfere with their future medical care. Whenever possible, the consent form will be given to them or mailed to the potential participant and study partner prior to the screening visit to allow the participant and study partner, as well as their family, to review the consent form in the privacy of their own home.

Should the participant be interested in participating, the study coordinator will set up a time to complete a phone interview (Phone Call #1). During the phone interview, subjects will provide verbal consent by expressing their interest in participating in the study. The phone interview will also explain that our participants will be randomized to one of two groups (initial disclosure of amyloid status; or delayed disclosure of amyloid status) and both groups will receive education and risk information for developing Alzheimer's disease dementia by age 85 based on age, gender, race, and family history of Alzheimer's disease dementia.

At the beginning of the participant's first in-person appointment (Visit #1), he/she will undergo an informed consent process and the consent form will be reviewed and signed by each participant and the study coordinator.

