Finally, the Everyday Discrimination Scale⁶² has been developed and will be used to assess perceived discrimination.

Step 6 – Phone call #3: Confirm eligibility/ineligibility + Schedule Scan

The study coordinator will call the participant within two weeks of Visit #2. If the participant is not screened out, he/she is eligible to continue with study participation. If eligible, the study coordinator will schedule the participant's PET scan at their site's imaging center, This visit should happen within approximately one month of Visit #2. A study coordinator will also call to schedule the disclosure session (Visit #4) within approximately two weeks from when the scan results are returned to Boston University.

Step 7 – Visit #3: Amyloid Neuroimaging Scan + Randomization

At this third in-person visit, participants who pass the above listed screening measures will undergo amyloid imaging via a scheduled PET scan at each site's respective imaging center. Participants will receive a single intravenous administration of approximately 370 MBq (10 mCi) of florbetapir F 18 amyloid imaging agent. Participants will be positioned in the PET scanner and at 50 ± minutes after injection.

Imaging data from this scan visit will be sent to Molecular NeuroImaging (MNI) electronically through a secure, already existing Web upload process. The imaging data will undergo a comprehensive quality control process consisting of both a technical and scientific quality control. MNI has already worked with, and received images from, all of the imaging centers in this study and has experience with all study site cameras. Imaging interpretations from MNI will be sent directly to our centralized data site, Boston University, labeled with study ID and de-identified personal health information.

Boston University will randomize the participants into either (1) Comparison/non-disclosure arm (D+): participants will learn the results of their amyloid scans at Visit #4 or (2) Intervention/disclosure arm (D-): participants will not learn their scan results at Visit #4, but will return for another in-person visit (Visit #7) after the completion of their 6-month follow-up (Visit #6) for a delayed disclosure visit. Participants are randomized with a 1:1 randomization for non-disclosure arm: disclosure arm. For participants who are randomized in the disclosure arm, their amyloid imaging results of "elevated" or "not elevated" amyloid will be returned to their respective sites.

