Based on this calculation, we have set a target to enroll n=50 in each of the 2 elevated amyloid groups (A+D-, A+D+). Due to a much lower than anticipated rate of amyloid positivity and a dropout rate of approximately 10%, we plan to enroll 370 total participants and achieve 100 completed 6 month visits to reach our group enrollment targets of n=50 for each elevated amyloid group.

VII. Risks and Discomforts

Psychological risks: We recognize that persons with normal cognition who learn they have elevated amyloid and an increased risk of developing AD dementia could experience psychological distress. We will monitor psychological well-being in our participants by pre-screening potential participants for anxiety and depression and administering standardized rating scales with pre-specified cut-off scores for affect and anxiety at scheduled follow-up visits after disclosure of PET amyloid imaging results. Additional monitoring and appropriate actions will be taken based on conversations between the study staff (clinician judgment) and participant.

For the 6-month visit digit-span task, we will examine how memory performance is affected by task instructions. Although the purpose of all the included cognitive measures is to assess the link between amyloid status and performance, during this task we will explicitly state this

relationship. Although we expect this to increase concerns about task performance, we do not expect this to create emotional distress. However, we will monitor responses. This will be done via conversations between the study staff (clinician judgment) and participant.

Deception: Mild deception will be used during the 6-month visit digit-span task. More specifically, during the initial trials of this task participants will be told that the purpose is to calibrate the equipment. No calibration will be conducted, but this instruction will reduce any evaluative concerns that may be felt by the participants. We do not anticipate this mild deception to create any distress. However, participants will be fully debriefed about this at the end of the study and their questions will be answered.

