Primary Analysis 1.1: For this aim we focus on one outcome, ADCS-PACC, and thus use an alpha level of 0.05 to determine statistical significance. First, we will obtain descriptive statistics for those who are in the D+ and D- groups among A+ subjects. Then, we will compare ADCS-PACC scores between D+ and D- groups among A+ subjects using a two-sided test of means. Next, we will compare D+ and D- groups on potential confounders. We will initially consider confounders due to the Covid-19 pandemic (as described below) and then consider other confounders (including age, education, premorbid function, experiences of discrimination). If any are significantly different between the two groups ($p < 0.05$), despite randomization, we will conduct regression analysis adjusting for those confounders that are different. Analyses will be repeated measures (6 wks. and 6 mos.) adjusting for baseline measure at time of randomization. We will focus on 6 month differences, but also check for time-averaged differences between D+ and D- groups. Check ADCS-PACC for normality. If normal, linear regression analysis for repeated measures can be used, specifically a mixed-effects model with repeated measures (MMRM). If not normal, we will use an appropriate transformation to make the distribution more normal. We will also conduct an Intention-to-Treat (ITT) analysis, which will incorporate information from those who drop out over the 6 months, assuming missing at random. This analysis will have better control of type 1 error and power. We will model time as a categorical measure, and the primary outcome will be the estimated difference (contrast) between the two groups (D+ and D-) at 6 months and secondarily the time-averaged difference. We will also apply a model with 3 repeated measures (baseline, 6 wks., 6 months) without adjustment for baseline ADCS-PACC to examine the full trend over time, but this will be a secondary analysis.

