Exploratory Analysis 1.3: The analysis will be the same as the primary analysis, but now conducted only in the African Americans in the study. If the hypothesis is true, we expect a larger difference, but the study is not powered for this subgroup analysis. To formally test whether African Americans have a greater response, we will perform analyses of the full group of A+ individuals, adding an interaction term to the model for race * disclosure group.

Aim 2: To determine whether disclosure of elevated brain amyloid will cause psychological distress.

Study Subjects: All Study Participants and the subgroup of A+ subjects

Outcomes: IES (Impact of Event Score), measured twice (6 wks., 6 mos.), and INI-AD, measured twice (6 wks., 6 mos.)

Hypothesis 2.1: At 6 weeks after disclosure, A+D+ participants will have greater IES scores and INI-AD scores than A-D+ or D- participants.

Analysis 2.1: Analysis will generally use the same methods as Aim 1. For this Aim, IES is the primary outcome for which we will use an alpha level of 0.05. INI-AD is a secondary outcome. Our main focus for this aim is contrasting scores between the A+D+ and A-D+ groups. We will also contrast the A+D+ and the D- groups (as long as the A+D- and A-D- exhibit similar outcomes). As in Aim 1, we will obtain

descriptive statistics between the two groups (A+D- and A-D+ for the first contrast and then A+D- vs the D- group). We will also evaluate the confounding effect of Covid-19 as described in Aim 1 and subsequently other potential confounders for these contrasts and incorporate if needed in further regression analyses. Note that there is no IES at baseline. So there is no adjustment for a baseline measure. The same holds true for INI-AD. One major difference here is that the IES and INI-AD are not normally distributed and cannot be transformed to become so. Thus, we will use generalized linear models fit with generalized estimating equations using a log link and a gamma distribution. If needed, we will add a value of 1 to all scores to shift the distribution away from zero and use a log transform on the data. We will focus on the differences at 6 weeks, but also evaluate the time-averaged differences.

Exploratory Hypothesis 2.2: Comparison of outcomes at 6 weeks and 6 months after disclosure will show African Americans to be equally vulnerable to psychological distress as measured by IES and INI-AD after amyloid imaging compared to all other racial and ethnic groups.

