Exploratory Analysis 2.2: Analyses will be the same as described above for IES and INI-AD applied to the subgroup of African Americans. To formally test whether effects are the same, we will add an interaction term to the model for race to evaluate whether African Americans experience similar distress as those in the study who are not African American.

Aim 3: To explore how amyloid imaging disclosure will impact preventative health behaviors, advance planning for health (e.g. long-term care insurance decisions) and well-being (e.g. stigma, quality of life and relationships).

Study Subjects: All Study Participants, contrasting D+ and D- participants. Additionally, we will compare the A+D+ subjects to the A-D+ subjects.

Outcomes: We will focus on outcomes at 6 months of follow up after disclosure.

Measures: We have several categories of behavior to examine.

- 1) Preventive Health Behaviors: diet, vitamin intake, physical exercise and mental exercise, medication changes
- 2) Advance Planning: long-term care insurance decisions, other insurance decisions, completion of advance directives
- 3) Well-being: stigma, quality of life and relationships, sharing of information

Aim 3 Hypotheses:

Preventive Health Behaviors:

D+ individuals will show equivalent probability of undertaking preventative health behavior changes as D- individuals.

A+D+ individuals will show a higher probability of undertaking more preventative health behavior changes than A-D+ individuals.

Advance Planning:

Advance planning will occur with a similarly low frequency in D+ and D- individuals.

Advance planning will occur more frequently for A+D+ individuals than A-D+ individuals.

Well-Being:

D+ individuals will report more sharing of information than D- individuals.

Sharing of information will not differ between A+D+ and A-D+ individuals.

D+ individuals will report more stigma compared to D- individuals. This effect will be modified by amyloid status. A+D+ individuals will report more worries about stigma than A-D+ individuals.

D+ individuals will report similar QOL compared to D- individuals. This effect will be modified by amyloid status. A+D+ individuals will report lower levels of quality of life than A-D+ individuals

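### African American recruitment is tied to one of four sites and no model includes site, so the exploratory race-by-disclosure tests mix race with any site difference in the disclosure effect.

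*SAP*

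**What the plan says.** Recruitment (Protocol, section III, Recruitment): "we will aim to recruit at least 25% African Americans through a partnership with Duke University". The next sentence adds: "We expect that half of the participants at the Duke site will be African Americans". Duke is one of four clinical sites. The documents give neither enrolment per site nor the split of African American participants across sites.

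Delivery (Protocol, section V, Step 8): a trained provider at each site carries out the disclosure session. Step 7 describes the allocation: "Participants are randomized with a 1:1 randomization for non-disclosure arm: disclosure arm". No stratification by site or race is described.

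Race tests: in SAP Exploratory Analysis 1.3, "we will perform analyses of the full group of A+ individuals, adding an interaction term to the model for race" by disclosure group. In Exploratory Analysis 2.2, for IES and INI-AD, "we will add an interaction term to the model for race to evaluate whether African Americans experience similar distress". The protocol (section VI, Data Analysis) also plans race-by-group interactions.

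Covariates: the protocol names sex, age and APOE genotype. The SAP (Primary Analysis 1.1) names age, education, premorbid function and experiences of discrimination, after the Covid-19 terms. Both lists are open-ended, but neither contains site, and the SAP does not mention site at all. Under the SAP a covariate enters only if it differs between D+ and D- at p<0.05.

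**The concern.** The recruitment plan builds in an association between race and site. If the effect of disclosure differs between Duke and the other sites, for example because providers conduct the session differently, a model with race-by-disclosure and no site terms assigns part of that difference to race. The SAP presents this interaction as its formal test of a greater African American response, so a site artefact could be read as racial vulnerability. In Aim 2 the hypothesis is that African American participants are equally vulnerable, so a site effect could also hide a real difference.

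The SAP's screening rule does not close the gap. Randomization tends to balance site between D+ and D-, so site would rarely pass the p<0.05 screen. The screen does not look at the association between race and site. Even if site passed, only its main effect would enter, with no site-by-disclosure term.

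**Working it through.** **Inputs.** From the protocol: 370 enrolled, at least 25% African American (taken as exactly 25%), half of Duke participants African American, four sites, PACC SD 2.2, 50 A+ completers per arm, design difference 1.25. Two-sided alpha is 0.05 (SAP). Assumed: Duke's share of enrolment (25% if the four sites are equal, up to 50%), the size of any site gap in the disclosure effect, the same race and site mix among the 100 A+ completers, and 1:1 allocation within each race-by-site cell.

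**The plan's own figure.** The detectable difference at 50 per group is 2.2 × √(2/50) × (1.960 + 0.842) = 1.23 by normal approximation and 1.245 by the t distribution. This agrees with the protocol's 1.25 and the SAP's 1.2451. The documents give no figure for the race interaction.

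**Race by site.** The target is 0.25 × 370 = 92.5 African American and 277.5 other participants. With Duke share s, Duke enrols 370s, of whom 185s are African American and 185s are not.

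**Shift in the race interaction.** Without site terms, shift = (proportion of African American participants at Duke − proportion of others at Duke) × site gap in the disclosure effect.

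| Duke share (assumed) | African American at Duke | Others at Duke | Shift, gap 0.5 | Shift, gap 1 | Shift, gap 1.25 |
|---|---|---|---|---|---|
| 25% | 46.25/92.5 = 50% | 46.25/277.5 = 17% | 0.17 | 0.33 | 0.42 |
| 35% | 64.75/92.5 = 70% | 64.75/277.5 = 23% | 0.23 | 0.47 | 0.58 |
| 50% | 92.5/92.5 = 100% | 92.5/277.5 = 33% | 0.33 | 0.67 | 0.83 |

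Per 1-point gap the shift is 27%, 37% or 53% of the 1.25-point design difference.

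**Precision with and without site.** SE = 2 × SD / √I. Without site terms I = n·p(1−p), with p the African American proportion. With site and site-by-disclosure terms I is the sum of n·p(1−p) over Duke and the other sites.

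- Without site: I = 100 × 0.25 × 0.75 = 18.75, SE = 4.4/√18.75 = 1.02.
- Duke 25%: I = 25 × 0.25 + 12.5 × 62.5/75 = 6.25 + 10.42 = 16.67, SE = 1.08.
- Duke 35%: I = 35 × 0.25 + 7.5 × 57.5/65 = 8.75 + 6.63 = 15.38, SE = 1.12.
- Duke 50%: I = 50 × 0.25 + 0 = 12.5, SE = 1.24.

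The interaction stays estimable because about half of Duke participants are not African American. The interaction detectable with 80% power (2.80 × SE) moves from 2.85 to 3.02, 3.14 or 3.49 points.

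**Effect on the test.** With a site gap of 1.25 points and no true race effect, the two-sided 5% test rejects about 7%, 9% or 13% of the time. Power for a true 1.25-point interaction without site terms is about 23%.

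**Within Duke only.** I = 6.25 to 12.5, so SE = 4.4/√6.25 = 1.76 down to 4.4/√12.5 = 1.24.

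**Constant site differences.** In Aim 1, D+ and D- are randomized within A+, so a site that scores everyone higher or lower affects both arms alike and largely cancels from the interaction. In Aim 2 the main contrast, A+D+ versus A-D+, compares amyloid groups that were not randomized, and the SAP states that IES and INI-AD have no baseline. If the site mix differs between those groups, a constant site difference need not cancel. The PACC figures above do not carry over to Aim 2, which uses a log link.

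**The case against.** These analyses are labelled exploratory, the SAP says the African American subgroup analysis is not powered, and the protocol will weigh estimates and intervals as well as p-values. The study also limits site differences: central audio quality control of PACC administration (Protocol, section IX), trained disclosure providers working from common reference curves, the A4 disclosure process, and consensus-built education material. A 1-point gap is 80% of the whole design difference (1/1.25) and nothing in the documents supports that size. Even at 1.25 points the excess of false rejections is modest.

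Most of this stands and keeps the point minor. It does not supply the missing site term. The audio quality control covers PACC administration, not the disclosure session, and the disclosure session is where a site difference in the disclosure effect would most plausibly arise.

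Three stronger readings are tempting, and the documents do not support them. A reader might infer that most African American participants come from Duke; with equal sites it is about half. A reader might combine an equal-sized Duke with all African American participants coming from it; that gives 46 of 370, or 12.5%, and breaks the 25% target. A reader might infer that race and site cannot be separated at all; that is true of the models as written, not of the data.

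**Conclusion.** The point holds as an inexpensive improvement to two exploratory analyses. Any site difference in the disclosure effect leaks into the race interaction at 0.33 to 0.67 PACC points per point of site gap. That range rests on Duke enrolling 25% to 50% of 370, half of Duke participants being African American, the 25% target being met exactly, and the same mix among A+ completers. The size of the gap is an assumption; the documents neither state nor imply one. Aim 2 is more exposed, because constant site differences may not cancel there, but that exposure cannot be quantified from the documents.

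A reader might infer that omitting site undermines the primary result. It does not: A+D+ versus A+D- is a randomized comparison and is not biased by leaving site out. Some between-site variation may stay in the residual, but baseline PACC adjustment should absorb much of it.

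**What to change.** 1. In the SAP, include site as a fixed effect in the PACC, IES and INI-AD models, whether or not it passes the D+ versus D- screen.
2. For Exploratory Analyses 1.3 and 2.2, pre-specify a sensitivity model with Duke-versus-other and its interaction with the disclosure group contrast, alongside the race interaction. In Aim 2 the contrast is the one being tested, such as A+D+ versus A-D+. The site main effect alone is not enough, because in Aim 1 the threat is a site difference in the disclosure effect.
3. State that a race difference will be interpreted as such only if the estimate is similar in that model.
4. Treat any race-by-disclosure estimate within Duke as descriptive. With an SE of about 1.2–1.8 points it cannot decide between race and site.
5. Report enrolment by site and race, so that readers can judge the overlap.

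Cost: SAP wording only, since the enrolling site is known for every participant. Four sites use three degrees of freedom, plus one for each site-by-contrast term. The SE of the PACC race interaction rises from about 1.02 to 1.08–1.24 points, a modest widening of an interval that is already wide.

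### Aim 2 asks whether disclosing elevated amyloid causes distress, but the SAP does not name the randomised contrast (A+D+ versus A+D-) for IES or INI-AD, and its only undisclosed comparison depends on an undefined similarity check

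*SAP*

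**What the plan says.** The SAP states the aim in causal terms: "Aim 2: To determine whether disclosure of elevated brain amyloid will cause psychological distress". Its hypothesis is "Hypothesis 2.1: At 6 weeks after disclosure, A+D+ participants will have greater IES scores and INI-AD scores than A-D+ or D- participants". Analysis 2.1 then sets out two contrasts. The first is the main one: "Our main focus for this aim is contrasting scores between the A+D+ and A-D+ groups". The second is conditional: "We will also contrast the A+D+ and the D- groups (as long as the A+D- and A-D- exhibit similar outcomes". The Data Analysis section of the protocol (VI) gives the same two contrasts and the same condition. Neither document says what counts as similar, at which visit, or what happens if the condition fails.

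On error control the SAP says "For this Aim, IES is the primary outcome for which we will use an alpha level of 0.05", with no order for the two contrasts. On population it says "Study Subjects: All Study Participants and the subgroup of A+ subjects", without attaching a contrast to the A+ subgroup. The descriptive step is written as "descriptive statistics between the two groups (A+D- and A-D+ for the first contrast and then A+D- vs the D- group", which matches neither planned contrast. On timing it says "We will focus on the differences at 6 weeks, but also evaluate the time-averaged differences", whereas the protocol (II, Specific Aims) places Hypothesis 2.1 at 6 months.

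A+D+ versus A+D- is named for ADCS-PACC in both documents, and for subjective memory in the protocol's Hypothesis 2.2 and the SAP's Hypothesis 1.2. Close to distress it appears only once, as an example in the protocol's sentence on exploratory race interactions.

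**The concern.** Disclosure is what was randomised. To learn what disclosure of an elevated result does, amyloid must be held at elevated and disclosure varied, which is A+D+ versus A+D-. The protocol uses this reasoning when it defends the Aim 1 comparison as one of randomised groups within a prespecified subgroup.

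The main Aim 2 contrast varies amyloid status within the disclosed arm. Amyloid status is not randomised; the protocol's background says it depends on age and correlates with *APOE* ε4. There is no baseline IES to adjust for. The contrast is a fair question in its own right, but it measures receiving an elevated rather than a not-elevated result. Relief in A-D+ would add to any harm in A+D+, and the contrast cannot separate the two.

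The second contrast does use undisclosed participants, but 70-75% of that comparator is A-. Whether it is run at all depends on a judgement made on the outcome data. If the plan is followed as written, a statement about the effect of disclosure could rest on a contrast that does not estimate it, while the one that does need not be reported.

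**Working it through.** **1. The plan's own figure.** The protocol's Power Calculation assumes an SD of 2.2 and 50 per A+ group, and states 80% power for 1.25 ADCS-PACC points; the SAP gives 1.2451. A two-sided t-test at 0.05 with 50 per group has 80% power for 0.566 SD, and 0.566 × 2.2 = 1.245. The figure reproduces. Aim 1 therefore already accepts about 0.57 SD for A+D+ versus A+D-. No sample size or power is given for IES or INI-AD.

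**2. Group sizes.** Inputs are 370 enrolled and about 10% dropout (protocol, Power Calculation), 1:1 allocation, and an A+ share of 25-30% (SAP, Analysis 1.1). Completers: 370 × 0.9 = 333, or 166.5 per arm.
- 30% A+: 49.95 A+ and 116.55 A- per arm; D- is 70% A-.
- 25% A+: 41.6 A+ and 124.9 A- per arm; D- is 75% A-.

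**3. Precision.** In SD units, SE = √(1/n₁ + 1/n₂). For example, √(1/49.95 + 1/49.95) = 0.200 and √(1/49.95 + 1/116.55) = 0.169. The detectable difference is for 80% power, two-sided 0.05, noncentral t.

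| Contrast | SE, 30% A+ | SE, 25% A+ | Detectable, 30% | Detectable, 25% |
|---|---|---|---|---|
| A+D+ vs A+D- | 0.200 | 0.219 | 0.57 SD | 0.62 SD |
| A+D+ vs A-D+ | 0.169 | 0.179 | 0.48 SD | 0.50 SD |
| A+D+ vs all D- | 0.161 | 0.173 | 0.45 SD | 0.49 SD |

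The SE of the randomised contrast is larger by a factor of 1.18 and 1.24 at 30% A+, and 1.22 and 1.26 at 25%.

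**4. On the scale of the planned model.** The SAP plans a log-link gamma model, and the documents give no IES mean or SD, so a coefficient of variation (CV) has to be assumed. SE(log ratio) = CV × √(1/n₁ + 1/n₂), and the detectable ratio of means is exp(2.80 × SE). For CV from 0.75 to 1.5:
- A+D+ vs A+D-: 1.52-2.32 (30% A+), 1.58-2.51 (25%).
- A+D+ vs A-D+: 1.43-2.04, 1.46-2.12.
- A+D+ vs all D-: 1.40-1.97, 1.44-2.07.

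**5. The similarity check.** Whatever rule is used, the 95% confidence interval for A+D- minus A-D- has a half-width of 0.33 SD (30% A+) to 0.35 SD (25%). As an illustration only: if similar meant p > 0.05, the power to see a gap of 0.2 SD would be 20-22%, and of 0.4 SD 60-65%. The true gap may be zero, and no bias is estimated here.

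**6. Testing order.** The two planned contrasts share the A+D+ group. Their correlation is (1/n₁)/(SE₁ × SE₂) = 0.0200/(0.169 × 0.161) = 0.73 at 30% A+. With each tested two-sided at 0.05 and no true effect (normal approximation, 2,000,000 draws), the chance of at least one false positive is about 8%. Adding A+D+ versus A+D- with no order would raise it to about 10.5%.

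**The case against.** The strongest reply is that the contrast is nearly specified already. The SAP lists the A+ subgroup as an Aim 2 population, the only disclosure comparison possible within it is D+ against D-, and Aim 2 largely takes over the Aim 1 methods. That suggests the analysis was intended. It does not give it a place in the hypothesis, the testing or the reporting.

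Second, D- participants do not know their amyloid status, so A+D- and A-D- may well report similar distress, and pooling them would be efficient. This is plausible. If it is so, removing the condition costs nothing; if not, a check with a half-width of about a third of an SD is a weak safeguard. Hypothesis 2.1 does name D- without a condition, but the condition in Analysis 2.1 governs what is run.

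Third, the SAP ranks the contrasts by calling one its main focus. That is a priority, not a testing order, although the 8% figure does assume that both are tested at 0.05. The 10.5% figure includes a contrast the plan does not name.

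Fourth, the protocol gives a reason to be wary of D-: waiting may raise distress. This stands, and it limits what A+D+ versus A+D- can mean, although the protocol adds that it was not seen in the team's earlier studies.

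Finally, the lack of a baseline IES affects every contrast, and the SAP says so openly. It matters most where the groups were not randomised.

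**Conclusion.** The concern holds, and the SAP should be changed. Aim 2 is causal, yet the contrast that uses the randomisation is left to inference for IES and INI-AD, and the only undisclosed comparison depends on an undefined look at the outcomes. A+D+ versus A-D+ remains legitimate and prespecified, but it is not the effect of disclosure.

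The randomised contrast is less precise: an SE 18-26% wider, with a detectable difference of 0.57-0.62 SD against 0.45-0.50 SD. At 50 per group this is the precision Aim 1 already accepts.

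These sizes assume 333 completers and 25-30% A+. The 10% loss is the 6-month figure, so somewhat more participants may be available at 6 weeks. SD units are a normal approximation to an outcome the SAP calls non-normal, and the ratios of means rest on an assumed CV. That the contrast is unnamed and the condition undefined depends on none of these assumptions.

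Two smaller points also stand: the descriptive sentence names the wrong groups, and the focus visit differs between protocol and SAP without explanation.

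**What to change.** - Name A+D+ versus A+D- as an unconditional contrast for IES and INI-AD, with a 95% confidence interval. Estimate it from one model in all participants with amyloid × disclosure × visit terms, keeping the SAP's adjustments for actual visit time and for visits after March 15, 2020.
- State its place in the testing order, for example after the prespecified A+D+ versus A-D+, and say that it was added late.
- Base the statement about disclosure on this contrast, worded as immediate versus delayed disclosure, because A+D- participants are waiting for their result.
- Keep A+D+ versus A-D+, interpret it as an elevated versus a not-elevated result, and adjust it for age, sex and *APOE*. The protocol names all three; the SAP's open list does not commit to sex or *APOE*.
- Run A+D+ versus all D- without the similarity condition, labelled as a mixed comparator.
- Correct the descriptive sentence to A+D+ and A-D+, then A+D+ versus D-.
- Reconcile the focus visit between protocol and SAP, and report the 6-week and 6-month contrasts separately. The repeated-measures model can give both, but Analysis 2.1 does not commit to the 6-month estimate.

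The cost is SAP wording, since the outcomes are already scheduled at both visits. The statistical price is the wider interval shown above. If waiting does raise distress in A+D-, the contrast could also be pulled toward zero, and the report should say so.
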